#### **6.8.4 Immune Gene Expression Analyses**

Castrate-resistant prostate cancer (CRPC) is a heterogeneous disease, with varying symptoms and overall survival ranging from several months to several years (Scher 2011). The ability to accurately predict outcome in men with CRPC is a crucial element in understanding response to treatment. While many studies have correlated clinical and laboratory variables with survival, the role that the immune system plays in controlling prostate cancer has not been fully studied, mainly due to the complexity of the immune system. Moreover, immune response assays can only interrogate discrete pathways 1 at a time, rather than assess the complex interaction between the various cellular and secreted components that comprise the entire immune system. Recent studies (Ross 2012, Olmos 2012) have shown that gene-expression profiling of peripheral blood cells can yield prognostic information with regards to control of CRPC.

An integrated and standardized system for collection, transport, and storage of whole blood specimens and isolation of either ribonucleic acid (RNA) or genomic deoxyribonucleic acid (DNA) (e.g., PAXgene®), will allow analyses of immune gene expression by detection of RNA or genetic analysis of germline DNA.

At screening, an 8.5 mL blood sample will be collected for baseline immune genetic analysis in a specialized tube that stabilizes intracellular DNA (e.g., PAXgene® Blood DNA Tube).

At all immune monitoring assessment time points, a 2.5 mL blood sample will be collected to assess immune gene expression profiles through analysis of intracellular RNAs in immune cells. These blood samples will be collected in a specialized tube containing an additive that stabilizes intracellular RNA (e.g., PAXgene® Blood RNA Tube).

Neither the subject nor the investigator will receive results from gene expression analysis.

#### **6.8.5 Sample Retention**

Samples from subjects who do not provide consent for additional optional research (Section 6.8.6) will be retained for up to 5 years following Dendreon's completion of the trial and then will be destroyed.

#### **6.8.6 Additional Optional Research**

Subjects will be given the opportunity to allow Dendreon to retain their blood samples (obtained for immune response, lot release, product characterization, and gene expression analysis) indefinitely and to use them for other testing. No additional blood draws will be required beyond those already being collected as part of the study. Additional research may include genetic testing and retained samples may be sent to outside laboratories for testing.

Retained samples will be used for research only, will not be sold, and will not be identified using subject names or other personal identifiers. Neither the subject nor the clinical trial site will receive results from additional testing.

## **6.9 Study Materials**

The clinical trial site will have a calibrated scale for recording body weight and a calibrated sphygmomanometer and thermometer for vital signs assessments. A current and fully stocked advanced cardiac life support cart will be immediately available on the premises. The clinical trial site will also have a refrigerated centrifuge, a monitored and alarmed refrigerator, and a freezer (-20°C or below) as well as containers and dry ice for shipment of blood samples.

The clinical trial site will provide all materials required for accurate documentation of subject visits and study activities.

Dendreon will provide an approved protocol and any required amendments or administrative letters, as well as the IB and electronic CRFs. Materials needed for the collection of laboratory samples, including immune monitoring samples, will be provided by Dendreon. Dendreon will also provide all applicable study specific training materials and reference binders.

## **7.0 ADVERSE EVENTS**

An AE is defined as any untoward medical occurrence in a subject while on study that does not necessarily have a causal relationship with the treatment. An AE can, therefore, be any unfavorable and unintended sign (e.g., abnormal laboratory finding), symptom, or disease temporally associated with the treatment, whether or not considered related to the treatment. Adverse events include exacerbation of a pre-existing illness, an increase in frequency or intensity of a pre-existing episodic event or condition, a condition detected or diagnosed after product administration (even though it may have been present prior to the start of the study) or a continuous persistent disease or symptoms present at screening that worsen following the start of the study.

### **7.1 Categories for Ranking Severity of Adverse Events**

The NCI CTCAE (**NCI 2010**) will be used to score AE severity. In general, the following general severity definitions apply:

*Mild (Grade 1):* The AE results in mild, easily tolerated symptoms, or is asymptomatic with clinical or diagnostic observations only. Intervention is not usually indicated.

*Moderate (Grade 2):* The AE produces moderate symptoms with discomfort sufficient to interfere with some aspect of the subject's normal daily activity. Minimal, local, or noninvasive intervention is required.

*Severe (Grade 3):* The AE is medically significant but not immediately life threatening, results in discomfort or disability which is incapacitating and prevents most normal daily activities, clearly damaging to the health, requiring hospitalization, prolongation of existing hospitalization or complicated treatment.

*Life Threatening (Grade 4):* The AE could reasonably result in death unless immediate medical intervention is undertaken.

*Fatal (Grade 5):* The AE results in death.

## 7.2 Relationship of Adverse Events to Study Treatments

The following categories will be used to determine relatedness of AEs to study treatments:

*None:* The AE is clearly related to other factors, such as the subject's clinical state, environmental factors, or other modes of therapy or concomitant medications administered to the subject.

*Possible:* The AE follows a reasonable temporal sequence from administration of study treatment, but could readily have been produced by the subject's clinical state, environmental factors, or other modes of therapy or concomitant medications administered to the subject.

*Probable:* The AE follows a reasonable temporal sequence from administration of study treatment and cannot readily have been produced by the subject's clinical state, environmental factors, or other modes of therapy or concomitant medications administered to the subject.

## 7.3 Serious Adverse Events

An SAE is defined as any adverse drug experience occurring at any dose that results in any of the following outcomes: death, a life threatening adverse drug experience, subject hospitalization or prolongation of an existing hospitalization, a persistent or significant disability/incapacity, or a congenital anomaly/birth defect. An important medical event that may not result in death, be life threatening, or require hospitalization may be considered a SAE when, based upon appropriate medical judgment, it may jeopardize the subject and may require medical or surgical intervention

to prevent one of the outcomes listed in this definition. Examples of such medical events include allergic bronchospasm requiring intensive treatment in an emergency room or at home, blood dyscrasias or convulsions that do not result in subject hospitalization, or the development of drug dependency or drug abuse.

### 7.3.1 Serious Adverse Event Collection and Reporting

All SAEs reported or observed, regardless of relationship to study treatments, and any remedial action(s) required, will be collected at all visits from registration through the post-treatment visit. Only treatment-related SAEs, seizures, and CVEs (regardless of causality) ongoing at the time of the post-treatment visit will be followed by the investigator until resolution, return to baseline, or the investigator determines no further improvement is expected. Only new treatment-related AEs and SAEs, seizures, and CVEs (regardless of causality) will be collected after the post-treatment visit.

All SAEs, whether or not considered related to study treatment, must be reported to Dendreon within 24 hours by entering the information on the electronic SAE report form. If access to the electronic SAE Form is unavailable for any reason, the SAE information must be reported to Dendreon or its designee within 24 hours by phone or by facsimile using the hardcopy SAE report form.

Dendreon Corporation  
Attn: Safety Manager  
[contact]  
[contact]  
After Hours: [contact]

Significant new information regarding an ongoing SAE and the resolution must be sent to Dendreon within 3 business days of awareness of the new information on either the electronic or hardcopy SAE report form.

The principal investigator is responsible for notifying the relevant IRB of any SAE that occurs in a subject participating at their clinical trial site and any Investigational New Drug (IND) Safety Reports issued by Dendreon unless otherwise instructed by relevant IRB policy.

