##### **6.4.1 Adverse Events and Serious Adverse Events**

Adverse events, including serious AEs (SAEs), seizures, and CVEs will be assessed at all visits and as needed during the course of the study.

All nonserious AEs and SAEs, regardless of relationship to study treatment, will be collected from registration through the post-treatment visit and will be recorded in the subject's medical record and on the CRF. Following the post-treatment visit, only new treatment-related AEs and SAEs will be recorded. Seizures and CVEs (regardless of causality) will be recorded throughout the study.

Only treatment-related AEs, SAEs, seizures, and CVEs (regardless of causality) ongoing at the time of the post-treatment visit will be followed by the investigator until resolution, return to baseline, or a determination by the investigator that no further improvement is expected.

See Section [7.0](#) for information regarding AE and SAE reporting.

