### **7.3.4 Death Reports**

Death is an expected outcome of this study. Deaths that meet any of the following criteria must be reported as an SAE:

- Deaths that occur within 30 days of receiving the last study treatment.
- Deaths that are the outcome of a SAE that occurs within 30 days from the last study treatment and are not due to disease recurrence.
- Deaths due to a seizure or CVE, regardless of causality, that occur at any time during the study.
- Deaths that occur at any time during the study and are considered by the investigator to be possibly or probably related to the study treatment.

Deaths that do not meet these criteria will not be reported as an SAE, but will be recorded on the CRF.

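### A death after the post-treatment visit from an unrelated SAE that began within 30 days of last treatment is reportable under Section 7.3.4, but nothing in the plan actively follows that SAE to its outcome

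*Protocol*

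**What the plan says.** Up to the post-treatment visit, collection does not depend on relationship. Section 7.3.1 states: "All SAEs reported or observed, regardless of relationship to study treatments, and any remedial action(s) required, will be collected at all visits from registration", and the period runs through that visit, which Section 3.1 places 30 to 37 days after the last study treatment.

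At the visit the rule narrows. Section 7.3.1: "Only treatment-related SAEs, seizures, and CVEs (regardless of causality) ongoing at the time of the post-treatment visit will be followed by the investigator". Section 6.4.1 has a near-identical sentence: "Only treatment-related AEs, SAEs, seizures, and CVEs (regardless of causality) ongoing at the time of the post-treatment visit will be followed by the investigator".

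After the visit it stays narrow. Section 7.3.1: "Only new treatment-related AEs and SAEs, seizures, and CVEs (regardless of causality) will be collected after the post-treatment visit". Section 6.4.1: "Following the post-treatment visit, only new treatment-related AEs and SAEs will be recorded", with the exception "Seizures and CVEs (regardless of causality) will be recorded throughout the study". Table 1 footnote j limits AE and SAE collection in long-term follow-up (LTFU) to treatment-related events, and SAP Section 4.5 repeats the restriction for the summaries.

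The death rule in Section 7.3.4 is wider. One of its four criteria for reporting a death as an SAE is: "Deaths that are the outcome of a SAE that occurs within 30 days from the last study treatment and are not due to disease recurrence". Any death that meets none of the four is still recorded on the CRF.

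**The concern.** The quoted criterion in Section 7.3.4 carries no relationship condition and no limit on when the death occurs. Deaths judged related, and deaths from a seizure or CVE, have criteria of their own, and so do deaths within 30 days of last treatment. What this criterion adds is the later death from an earlier SAE that was judged unrelated and was neither a seizure nor a CVE. That is the class of SAE which Section 7.3.1 stops following at the post-treatment visit. A site can comply fully with 7.3.1 and have no planned means of learning that a death it must report under 7.3.4 was the outcome of such an SAE.

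At stake is the completeness of the fatal-outcome record for SAEs that began on or shortly after treatment. An SAE may stay coded as ongoing when it was in fact fatal. It would then be absent from SAP table 14.3.1.6, which counts adverse events leading to death. Safety is a secondary objective (Section 2.2).

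**Working it through.** The plan gives no figure to reproduce. The check puts the rules on one timeline, with day 0 as the last study treatment and the post-treatment visit on day 30 to 37.

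**Which fatal cases are covered?**

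| Case | Reportable under 7.3.4? | Captured by 6.4.1 / 7.3.1? |
|---|---|---|
| (a) Death by day 30, any cause | Yes, first criterion | Yes, before the visit |
| (b) SAE onset by day 30, death after day 30 but before the visit | Yes, unless disease recurrence | Yes, all SAEs are collected through the visit |
| (c) SAE treatment-related, or a seizure or CVE; open at the visit, fatal later | Yes | Yes, followed after the visit |
| (d) SAE unrelated, not a seizure or CVE, onset by day 30; open at the visit, fatal later, not disease recurrence | Yes, second criterion | No active follow-up, and not a new event to collect |

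Only (d) is open.

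**A worked example of (d).** Onset is on day 25, the visit on day 33 and death on day 50.

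1. The SAE is on record, because it began before the visit. It has been observed for 33 − 25 = 8 days when follow-up stops.
2. Across all onsets from day 0 to day 30 and visits from day 30 to day 37, the observed time runs from 30 − 30 = 0 to 37 − 0 = 37 days.
3. The first LTFU visit is 3 months after the post-treatment visit, with a window of ± 2 weeks (Table 1 and footnote f). Taking 3 months as about 91 days, it falls near day 33 + 91 = 124, window day 110 to 138.
4. If the site hears of the death only at that contact, the delay is between 110 − 50 = 60 and 138 − 50 = 88 days. Section 7.3.1 asks for SAE reports within 24 hours.

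**Do other provisions close case (d)?**

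- The update rule in Section 7.3.1 covers significant new information on an ongoing SAE, within 3 business days. It has no relationship limit and no end date, but it starts from the site's awareness, and no contact is required to create that awareness for an unrelated SAE.
- Survival status is assessed every 3 months, and the date and cause of death go on the CRF (Section 6.6). This captures the death. Nothing requires the cause to be compared with earlier open SAEs. If the only source is a death index, Section 6.6 notes that it gives the date alone.
- LTFU contact moves to telephone after the first LTFU visit following the end of enzalutamide (Table 1 footnotes i and m). Contact continues, but its content does not include unrelated SAEs.
- The final-status contact in Section 4.3.4 concerns men who leave the study, and its continuing follow-up is again for related AEs.
- The list in Section 6.4.1 could be parsed so that its relationship limit governs AEs only, which would leave all SAEs followed. Section 7.3.1 puts the limit directly on SAEs, and the preceding paragraph of 6.4.1 limits SAEs recorded after the visit in the same way, so that reading is not secure.

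These provisions reduce the gap and do not close it.

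**The case against.** The strongest reply is that this is a small mismatch of wording. Limiting follow-up of unrelated events looks deliberate, since it recurs across both documents. The SAE itself is already reported. Section 7.3.4 sends every death either to an SAE report or to the CRF, so a site must test each known death against the criteria. A fatal outcome of an SAE already on file is arguably not a new event, and the 3-business-day rule would then apply. Section 7.2 reserves the unrelated category for events clearly due to other factors, so doubtful SAEs will tend to be called possible and followed. Causes of death also appear in the disposition summary and in SAP table 14.3.5.

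All of this stands as a limit on size. It does not remove the conflict, because each safeguard works only once someone learns that the death came from that SAE.

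A reader might also infer more than the documents support:

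- **That nothing unrelated is collected after the visit, or that deaths are lost.** Seizures and CVEs of any cause, survival status and cause of death are all still collected.
- **That follow-up would differ between arms because one group takes two drugs at once.** The visit is timed from the last study treatment. Men in either arm who follow the schedule have completed sipuleucel-T and end on enzalutamide alone. Such a contrast could arise only among men who stop early.
- **That the data monitoring committee would be deprived of a notice it should receive.** In Section 7.4.1 the relatedness qualifier may also apply to the fatal-event notice, and the fatal-event criterion for suspending enrolment covers only deaths at least possibly related.

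**Conclusion.** The conflict holds in a narrow form. A death after the post-treatment visit that results from an unrelated, non-seizure, non-CVE SAE with onset within 30 days of last treatment, and is not due to disease recurrence, must be reported under Section 7.3.4. Sections 6.4.1 and 7.3.1, Table 1 footnote j and SAP Section 4.5 provide no active follow-up that would identify it. What can be missed or delayed is the link to the earlier SAE, the SAE report, and the count in table 14.3.1.6.

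The number of men cannot be derived. The documents give no rate of unrelated SAEs open at the visit, and none for those that later prove fatal. A case must meet every condition in row (d), and 52 men were enrolled (SAP Section 3.1), so the number is probably small. Overall survival, power and the primary immune-response analysis are unaffected. The delay of 60 to 88 days belongs to the example and assumes that the site hears nothing before the first LTFU contact.

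This is a reporting inconsistency worth repairing because the repair is cheap.

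**What to change.** Reconcile Sections 6.4.1 and 7.3.1, Table 1 footnote j and SAP Section 4.5 with Section 7.3.4. State that, for any SAE with onset up to 30 days after the last study treatment and still ongoing at the post-treatment visit, whatever its relationship:

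- the final outcome, including death, is ascertained at the existing 3-monthly LTFU contacts;
- a fatal outcome is reported as Section 7.3.4 requires, whenever it occurs;
- the fatal outcome is counted in SAP table 14.3.1.6.

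Keep the relationship limit for nonserious AEs and for events with later onset. The present follow-up of related events, seizures and CVEs is unchanged.

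A cross-reference from 7.3.1 to 7.3.4 alone would align the wording, but it would still leave no one asked to obtain the outcome.

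The cost is wording in four places and a few more open SAEs to query at contacts that already take place. No extra visit is needed.

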### 7.3.2 Cerebrovascular Events

All CVEs, regardless of causality, severity, or outcome, will be reported as AEs and SAEs when they occur from registration until the subject ceases study participation.

### **7.3.3 Seizures**

All seizures, regardless of causality, severity, or outcome, will be reported as AEs and SAEs when they occur from registration until the subject ceases study participation.

### **7.3.4 Death Reports**

Death is an expected outcome of this study. Deaths that meet any of the following criteria must be reported as an SAE:

- Deaths that occur within 30 days of receiving the last study treatment.
- Deaths that are the outcome of a SAE that occurs within 30 days from the last study treatment and are not due to disease recurrence.
- Deaths due to a seizure or CVE, regardless of causality, that occur at any time during the study.
- Deaths that occur at any time during the study and are considered by the investigator to be possibly or probably related to the study treatment.

Deaths that do not meet these criteria will not be reported as an SAE, but will be recorded on the CRF.

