### Sequential Arm

Subjects will receive sipuleucel-T followed by enzalutamide (160 mg orally once daily). Enzalutamide treatment will start approximately 10 weeks after the first infusion of sipuleucel-T and continue for 52 weeks or until disease progression or unacceptable toxicity, whichever occurs first. Subjects randomized to the sequential arm who do not receive at least one partial ( $> 0$  mL) infusion of sipuleucel-T will not receive any enzalutamide treatment, will undergo a post-treatment visit, and will enter the LTFU phase.

[figure not shown]
**After 52 weeks of enzalutamide treatment provided by Dendreon, subjects in either treatment arm may continue to receive enzalutamide obtained from other sources at the discretion of their treating physician. Dendreon cannot provide enzalutamide beyond the protocol-specified duration of 52 weeks.**

During the active phase, subjects in both arms will undergo a standard 1.5 to 2.0 blood volume leukapheresis, followed approximately 3 days later by an intravenous (IV) infusion of sipuleucel-T. This process will occur a total of 3 times at approximately 2-week intervals. A course of sipuleucel-T treatment comprises 3 infusions. Immune monitoring blood samples will be drawn and clinical and safety assessments will be performed at screening, preleukapheresis visits 2 and 3, and weeks 6, 10, 14, 20, 26, 40, and 52, with the timing of visits based on the date of the first sipuleucel-T infusion. Immune monitoring blood samples will also be drawn following each sipuleucel-T infusion. Additional assessments including physical examinations, vital signs, ECOG performance status (see [Appendix 1](#)), AE monitoring, anticancer therapies, first opioid use for cancer-related pain, laboratory tests (e.g., hematology and serum chemistries), and PSA monitoring will be performed at the times shown in [Table 1](#).

During the LTFU phase, safety (treatment-related AEs, seizures, and CVEs), survival status, PSA, ECOG performance status, first opioid use for cancer-related pain (if applicable), and anticancer therapies will be assessed every 3 months until the subject's death or until Dendreon terminates the study.

The study design is illustrated in [Figure 1](#).

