## **5.0 STUDY TREATMENTS**

### **5.1 Handling Study Treatments**

Study treatments must be stored, handled, and prepared as specified by the sipuleucel-T investigator's brochure (IB, **Sipuleucel-T 2013**) and the enzalutamide prescribing information (**Xtandi 2012**). Dendreon should be notified immediately if concerns regarding the quality or appearance of the study treatments arise.

Accountability documentation, including receipt, storage and applicable storage conditions, administration, destruction and use of required processes must be maintained to ensure the study treatments are accurately administered.

Dendreon will supply the study treatments (sipuleucel-T, enzalutamide). Enzalutamide will be labeled with protocol-specific information, including the statement "Caution: New Drug-Limited by United States law to investigational use."

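### Protocol 7.3.1 and 7.3.4 conflict on SAE reporting of some active-phase deaths; both arms are affected, and the sequential arm has one further gap between its two treatments

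*Protocol*

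**What the plan says.** Protocol 7.3 opens: "An SAE is defined as any adverse drug experience occurring at any dose that results in any of the following outcomes: death". Section 7.3.1 provides that SAEs, regardless of relationship, "will be collected at all visits from registration through the post-treatment visit", and adds: "All SAEs, whether or not considered related to study treatment, must be reported to Dendreon within 24 hours". Section 6.4.1 gives the same collection period.

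Section 7.3.4 lists four criteria under which a death must be reported as an SAE:

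1. "Deaths that occur within 30 days of receiving the last study treatment".
2. "Deaths that are the outcome of a SAE that occurs within 30 days from the last study treatment and are not due to disease recurrence".
3. Death due to a seizure or cerebrovascular event, at any time in the study.
4. Death at any time that the investigator considers possibly or probably related to study treatment.

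It closes: "Deaths that do not meet these criteria will not be reported as an SAE, but will be recorded on the CRF". Neither section refers to the other.

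Section 5.1 names sipuleucel-T and enzalutamide as the study treatments. Section 3.1 starts enzalutamide 2 weeks before the first leukapheresis in the concurrent arm. For the sequential arm it says: "Enzalutamide treatment will start approximately 10 weeks after the first infusion of sipuleucel-T". In both arms the active phase ends at the post-treatment visit, 30 to 37 days after the last study treatment.

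**The concern.** The period in 7.3.1 follows the calendar, from registration to the post-treatment visit. Criteria 1 and 2 of 7.3.4 follow dosing. Where the active phase runs on but no study treatment has been given in the preceding 30 days, an unrelated death falls under a duty to report in one section and an exclusion in the other.

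Two things are at stake. A site may leave such a death off the 24-hour pathway, because recording it on the CRF carries no such clock. And because dosing differs by arm by design, the same kind of death can count as an SAE in one arm and not in the other. The SAP tabulates SAEs by treatment group (section 4.5.1; tables 14.3.1.8 and 14.3.1.9).

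**Working it through.** The plan states no figure for this, so the check is date arithmetic. Day 0 is the first infusion.

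**Inputs**
- Infusions at about days 0, 14 and 28 (Protocol 3.1, intervals of about 2 weeks).
- Leukapheresis about 3 days before each infusion (3.1).
- Sequential-arm enzalutamide from about day 70 (10 weeks), with a dispensing window of ±7 days (Table 1).
- Concurrent-arm enzalutamide from about day −3 − 14 = −17.
- Criterion 1 lasts 30 days after the most recent study treatment.

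**Gap between treatments, sequential arm only.** Uncovered days = enzalutamide start − last infusion − 30.

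| Infusions given | Last infusion | Coverage ends | Gap, start on day 70 | Gap, start on day 63 to 77 |
|---|---|---|---|---|
| 3 | day 28 | day 58 | 12 | 5 to 19 |
| 2 | day 14 | day 44 | 26 | 19 to 33 |
| 1 | day 0 | day 30 | 40 | 33 to 47 |

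A late third infusion shortens the gap. If it is given on day 40 and enzalutamide starts on day 70, the gap is 70 − 40 − 30 = 0. A concurrent-arm subject still taking daily enzalutamide has no such gap.

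**Before first study treatment, both arms.** The concurrent arm is uncovered from registration to the first enzalutamide dose, the sequential arm from registration to the first infusion. Neither length is stated. In the sequential arm this includes the roughly 3 days from first leukapheresis to infusion, if leukapheresis is not itself a study treatment.

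**Before the post-treatment visit, both arms.** The uncovered days are 31 to 37, so at most 37 − 30 = 7, and none if the visit is on day 30.

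**After early enzalutamide discontinuation, both arms.** Under 4.3.2, subjects who stop after 3 infusions and at least 10 weeks of enzalutamide continue active-phase assessments. If they stop at exactly 10 weeks and stay in the active phase to week 52 (day 364):
- concurrent: the stop is on day −17 + 70 = 53, leaving 364 − 53 − 30 = 281 uncovered days;
- sequential: the stop is on day 70 + 70 = 140, leaving 364 − 140 − 30 = 194 uncovered days.

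These are extreme cases. The protocol does not say how 4.3.2 fits with a post-treatment visit fixed at 30 to 37 days after last treatment.

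**Split between arms for a fully treated subject.** Let x be the days from registration to the first scheduled procedure (assumed 0 to 28, the same in both arms) and t the uncovered days before the post-treatment visit (0 to 7). Uncovered days are x + 3 + 12 + t in the sequential arm and x + t in the concurrent arm. With x = 0 and t = 0 this is 15 against 0, a sequential share of 100%. With x = 28 and t = 7 it is 50 against 35, a share of 50/85 = 59%. If instead the first leukapheresis falls on the same day after registration in both arms (assumed day 14 to 28), the share runs from 100% down to 50/(50 + 21) = 70%.

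**The case against.** The strongest reply is that 7.3.4 is a deliberate exception. It is specific to deaths and begins by noting that death is expected in this study, so it can be read as overriding the general rule. That reading is available, but the text does not state it, and it would not remove the difference between arms. Expectedness is handled separately, for expedited reporting to the regulator, in 7.3.4.1.

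Other replies stand in part:

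- Criteria 2 to 4 still capture many deaths in these periods. A reader might infer that any death at week 9 is an SAE in one arm and not in the other. That holds only for deaths outside criteria 2 to 4, comparing a concurrent-arm subject on enzalutamide with a sequential-arm subject between treatments.
- A life-threatening event or hospitalization before death is an SAE in its own right and reportable within 24 hours. What can escape is a death with no earlier serious event, such as a sudden death at home.
- Deaths also appear outside the SAE tables, in SAP tables 14.3.1.6 and 14.3.5 and listing 16.2.6.1.
- A sequential-arm subject who dies before any leukapheresis is outside the safety population (Protocol 8.3, SAP 3.2.3), so that part of the pre-treatment period cannot distort the SAE tables.
- Whether leukapheresis is a study treatment is unclear. Section 5.1 does not list it, but 5.2.4 places it under the sipuleucel-T treatment heading.
- The SAE definition in 7.3 speaks of a drug experience, which fits poorly with a death before any dose. Sections 6.4.1 and 7.3.1 nonetheless collect SAEs from registration, regardless of relationship.

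**Conclusion.** The conflict is real but narrow. For the deaths described, 7.3.1 requires a 24-hour SAE report and 7.3.4 excludes it. Both arms are affected. The between-treatment gap is particular to the sequential arm: about 12 days at nominal timing, 5 to 19 with the visit window, longer with fewer infusions and shorter with a late third one.

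A reader might infer that the uncovered time lies almost wholly in the sequential arm. The documents do not support that. Under the assumed delays its share for a fully treated subject is 59% to 100%. It reaches 100% only if the concurrent arm has no pre-treatment delay and the post-treatment visit is on day 30. After early enzalutamide discontinuation the concurrent arm's uncovered time may be the longer. Nor do product failures simply lengthen the gap: a failure that only delays the third infusion, with enzalutamide still started on day 70, shortens it.

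No immune-response, PSA or survival analysis is touched. With 52 subjects (25 concurrent, 27 sequential; SAP 3.1), few deaths should fall in these periods, but each is a safety event that should be handled the same way in both arms. The result assumes nominal timing and that the last study treatment means the most recent dose of either product.

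**What to change.** Reconcile 7.3.4 with 7.3.1 so that one rule covers deaths from registration through the post-treatment visit. One sentence would do. For example, every death in that period is reported as an SAE, and the four listed criteria apply only afterwards. The same edit should say whether leukapheresis counts as a study treatment and when the active phase ends for subjects who stop enzalutamide early under 4.3.2.

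In the SAP, build tables 14.3.1.8 and 14.3.1.9 on that rule in both arms. Enrollment has closed, so the edit cannot restore 24-hour reports already missed, but the tables can still be made uniform from the CRF death data.

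The cost is a few extra SAE forms, including some for deaths from disease, and a short programming rule for the tables.
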